Chronic kidney disease stages I-III; n (%)*	284 (8.9%)	276 (8.6%)	0.0010	284 (4.9%)	272 (4.7%)	0.0009	568 (6.3%)	548 (6.1%)	0.0083
Chronic kidney disease stages IV-V, ESRD; n (%)	103 (3.2%)	70 (2.2%)	0.0061	89 (1.5%)	55 (0.9%)	0.0055	192 (2.1%)	125 (1.4%)	0.0534
Premature menopause; n (%)	3 (0.1%)	7 (0.2%)	-0.0026	5 (0.1%)	10 (0.2%)	-0.0026	008 (0.1%)	017 (0.2%)	-0.0258
Oophorectomy; n (%)	3 (0.1%)	5 (0.2%)	-0.0026	7 (0.1%)	3 (0.1%)	0.0000	010 (0.1%)	008 (0.1%)	0.0000
COPD; n (%)*	411 (12.9%)	401 (12.5%)	0.0011	584 (10.0%)	594 (10.2%)	-0.0006	995 (11.0%)	995 (11.0%)	0.0000
Asthma; n (%)*	294 (9.2%) 123 (3.8%)	300 (9.4%) 125 (3.9%)	-0.0007 -0.0005	461 (7.9%) 171 (2.9%)	490 (8.4%) 152 (2.6%)	-0.0018 0.0018	755 (8.4%) 294 (3.3%)	790 (8.8%) 277 (3.1%)	-0.0143 0.0114
Obstructive sleep apnea; n (%)* Syncope; n (%)*	131 (4.1%)	139 (4.3%)	-0.0003	236 (4.1%)	236 (4.1%)	0.0018	367 (4.1%)	375 (4.2%)	-0.0050
Falls; n (%)*	266 (8.3%)	272 (8.5%)	-0.0010	146 (2.5%)	157 (2.7%)	-0.0012	412 (4.6%)	429 (4.8%)	-0.0030
VTE; n (%)	47 (1.5%)	72 (2.3%)	-0.0058	78 (1.3%)	119 (2.0%)	-0.0012	125 (1.4%)	191 (2.1%)	-0.0534
Gait abnormality; n (%)*	282 (8.8%)	305 (9.5%)	-0.0023	405 (7.0%)	373 (6.4%)	0.0023	687 (7.6%)	678 (7.5%)	0.0038
Osteopenia; n (%)*	1,200 (37.5%)	1,203 (37.6%)	-0.0002	1,585 (27.3%)	1,626 (28.0%)	-0.0013	2,785 (30.9%)	2,829 (31.4%)	-0.0108
Hip and femur fractures; n (%)*	86 (2.7%)	98 (3.1%)	-0.0023	113 (1.9%)	122 (2.1%)	-0.0014	199 (2.2%)	220 (2.4%)	-0.0133
Vertebral fractures; n (%)*	298 (9.3%)	304 (9.5%)	-0.0007	543 (9.3%)	527 (9.1%)	0.0007	841 (9.3%)	831 (9.2%)	0.0035
Other Fractures; n (%)*	141 (4.4%)	142 (4.4%)	0.0000	206 (3.5%)	206 (3.5%)	0.0000	347 (3.8%)	348 (3.9%)	-0.0052
Combined comorbidity score, 450 days*									
mean (sd)	0.70 (1.83)	0.68 (1.82)	0.0110	0.40 (1.40)	0.40 (1.37)	0.0000	0.51 (1.57)	0.50 (1.54)	0.0064
median [IQR]	0.00 [-1.00, 1.00]	0.00 [-1.00, 1.00]	0.0000	0.00 [-1.00, 1.00]	0.00 [0.00, 1.00]	0.0000	0.00 (1.57)	0.00 (1.54)	0.0000
Frailty Score: Empirical Version 365 days as Categories*< 0.12908; n (%)	1,492 (46.7%)	1,502 (47.0%)	-0.0004	2,738 (47.1%)	2,740 (47.1%)	0.0000	4,230 (46.9%)	4,242 (47.1%)	-0.0040
	866 (27.1%)	846 (26.5%)	0.0012	1,570 (27.0%)	1,563 (26.9%)	0.0000	2,436 (27.0%)	2,409 (26.7%)	0.0068
>= 0.1631167; n (%)	840 (26.3%)	850 (26.6%)	-0.0006	1,508 (25.9%)	1,513 (26.0%)	-0.0002	2,348 (26.0%)	2,363 (26.2%)	-0.0046
Medication Use	0.10 (=0.070)	()		-, (=,-)	-, (=,		_,,,,,	=,= ++ (= ++= ++)	
Use of Calcitonin (salmon); n (%)	1 (0.0%)	0 (0.0%)	0.0000	243 (4.2%)	213 (3.7%)	0.0025	244 (2.7%)	213 (2.4%)	0.0190
Use of oral corticosteroids; n (%)*	779 (24.4%)	770 (24.1%)	0.0006	1,542 (26.5%)	1,540 (26.5%)	0.0000	2,321 (25.7%)	2,310 (25.6%)	0.0023
Use of antidepressants; n (%)*	836 (26.1%)	821 (25.7%)	0.0008	1,522 (26.2%)	1,542 (26.5%)	-0.0006	2,358 (26.2%)	2,363 (26.2%)	0.0000
Use of anticonvulsants; n (%)*	353 (11.0%)	387 (12.1%)	-0.0032	669 (11.5%)	689 (11.8%)	-0.0009	1,022 (11.3%)	1,076 (11.9%)	-0.0187
Use of beta blocker OR calcium channel blocker; n (%)*	1,013 (31.7%)	1,009 (31.6%)	0.0002	1,855 (31.9%)	1,884 (32.4%)	-0.0009	2,868 (31.8%)	2,893 (32.1%)	-0.0064
Use of PPIs; n (%)*	968 (30.3%)	962 (30.1%)	0.0004	1,845 (31.7%)	1,863 (32.0%)	-0.0005	2,813 (31.2%)	2,825 (31.3%)	-0.0022
Use of opioids; n (%)*	1,100 (34.4%)	1,111 (34.7%)	-0.0005	2,080 (35.8%)	2,074 (35.7%)	0.0002	3,180 (35.3%)	3,185 (35.3%)	0.0000
Use of antipsychotics; n (%)*	58 (1.8%)	56 (1.8%)	0.0000 0.0007	97 (1.7%)	86 (1.5%) 660 (11.3%)	0.0016 0.0000	155 (1.7%) 957 (10.6%)	142 (1.6%)	0.0079
Use of anxiolytics/hypnotics; n (%)* Use of dementia meds; n (%)*	301 (9.4%) 109 (3.4%)	293 (9.2%)	-0.0016	656 (11.3%) 188 (3.2%)	200 (3.4%)	-0.0011	297 (3.3%)	953 (10.6%) 317 (3.5%)	0.0000 -0.0110
Use of antiparkinsonian meds; n (%)*	109 (3.4%)	117 (3.7%) 105 (3.3%)	-0.0016	188 (3.2%)	156 (2.7%)	0.0001	260 (2.9%)	261 (2.9%)	0.0000
Use of Benzodiazepine; n (%)*	403 (12.6%)	402 (12.6%)	0.0000	1,192 (20.5%)	1,196 (20.6%)	-0.0002	1,595 (17.7%)	1,598 (17.7%)	0.0000
All antidiabetic medications; n (%)*	341 (10.7%)	351 (11.0%)	-0.0009	589 (10.1%)	583 (10.0%)	0.0003	930 (10.3%)	934 (10.4%)	-0.0033
ACEI/ARB; n (%)*	1,218 (38.1%)	1,241 (38.8%)	-0.0011	2,250 (38.7%)	2,256 (38.8%)	-0.0002	3,468 (38.5%)	3,497 (38.8%)	-0.0062
Use of Anticoagulants; n (%)*	176 (5.5%)	183 (5.7%)	-0.0008	282 (4.8%)	315 (5.4%)	-0.0027	458 (5.1%)	498 (5.5%)	-0.0179
Use of Amiodarone; n (%)	25 (0.8%)	19 (0.6%)	0.0024	48 (0.8%)	37 (0.6%)	0.0024	073 (0.8%)	056 (0.6%)	0.0240
Digoxin; n (%)	52 (1.6%)	58 (1.8%)	-0.0015	97 (1.7%)	92 (1.6%)	0.0008	149 (1.7%)	150 (1.7%)	0.0000
Use of Diuretics; n (%)*	1,021 (31.9%)	1,041 (32.6%)	-0.0012	1,865 (32.1%)	1,857 (31.9%)	0.0004	2,886 (32.0%)	2,898 (32.1%)	-0.0021
Use of Aspirin; n (%)	25 (0.8%)	21 (0.7%)	0.0012	55 (0.9%)	56 (1.0%)	-0.0010	080 (0.9%)	077 (0.9%)	0.0000

651 (20.4%) 315 (9.8%) 23 (0.7%) ,427 (44.6%) 746 (23.3%)	643 (20.1%) 318 (9.9%) 16 (0.5%) 1,443 (45.1%) 847 (26.5%)	0.0007 -0.0003 0.0026 -0.0007 -0.0064	1,198 (20.6%) 743 (12.8%) 64 (1.1%) 2,677 (46.0%) 2,079 (35.7%)	1,155 (19.9%) 751 (12.9%) 66 (1.1%) 2,656 (45.7%)	0.0016 -0.0003 0.0000 0.0004	1,849 (20.5%) 1,058 (11.7%) 087 (1.0%) 4,104 (45.5%)	1,798 (19.9%) 1,069 (11.9%) 082 (0.9%) 4,099 (45.5%)	0.0149 -0.0062 0.0103 0.0000
23 (0.7%) ,427 (44.6%) 746 (23.3%)	16 (0.5%) 1,443 (45.1%)	0.0026 -0.0007	64 (1.1%) 2,677 (46.0%)	66 (1.1%) 2,656 (45.7%)	0.0000	087 (1.0%)	082 (0.9%)	0.0103
,427 (44.6%) 746 (23.3%)	1,443 (45.1%)	-0.0007	2,677 (46.0%)	2,656 (45.7%)		· /	· /	
746 (23.3%)					0.0004	4,104 (45.5%)	4 099 (45 5%)	0.0000
	847 (26.5%)	-0.0064	2,079 (35.7%)	2.246 (20.60/)				
2.08 (18.32)				2,246 (38.6%)	-0.0048	2,825 (31.3%)	3,093 (34.3%)	-0.0639
2.08 (18.32)								
2.08 (18.32)								
	21.98 (16.47)	0.0057	20.71 (16.23)	20.85 (15.42)	-0.0088	21.20 (17.00)	21.25 (15.80)	-0.0030
00 [8.00, 31.00]	18.00 [10.00, 30.00]	0.0000	17.00 [9.00, 28.00]	18.00 [10.00, 28.00]	-0.0632	17.35 (17.00)	18.00 (15.80)	-0.0396
12.76 (9.40)	12.86 (8.99)	-0.0109	10.14 (7.52)	10.11 (7.03)	0.0041	11.07 (8.24)	11.09 (7.78)	-0.0025
00 [6.00, 17.00]	11.00 [7.00, 16.25]	-0.1087	9.00 [5.00, 14.00]	9.00 [5.00, 13.00]	0.0000	9.35 (8.24)	9.71 (7.78)	-0.0449
0.42 (0.91)	0.42 (0.93)	0.0000	0.34 (0.85)	0.34 (0.89)	0.0000	0.37 (0.87)	0.37 (0.90)	0.0000
00 [0.00, 1.00]	0.00 [0.00, 1.00]	0.0000	0.00 [0.00, 0.00]	0.00 [0.00, 0.00]	0.0000	0.00 (0.87)	0.00 (0.90)	0.0000
0.16 (0.53)	0.18 (0.61)	-0.0350	0.78 (2.88)	0.77 (2.89)	0.0035	0.56 (2.33)	0.56 (2.35)	0.0000
00 [0.00, 0.00]	0.00 [0.00, 0.00]	0.0000	0.00 [0.00, 0.00]	0.00 [0.00, 0.00]	0.0000	0.00 (2.33)	0.00(2.35)	0.0000
18 (0.6%)	20 (0.6%)	0.0000	54 (0.9%)	53 (0.9%)	0.0000	072 (0.8%)	073 (0.8%)	0.0000
326 (10.2%)	347 (10.9%)	-0.0022	721 (12.4%)	732 (12.6%)	-0.0006	1,047 (11.6%)	1,079 (12.0%)	-0.0124
0.23 (1.14)	0.26 (1.02)	-0.0277	1.72 (2.75)	1.71 (3.02)	0.0035	1.19 (2.31)	1.20 (2.50)	-0.0042
00 [0.00, 0.00]	0.00 [0.00, 0.00]	0.0000	1.00 [0.00, 2.00]	1.00 [0.00, 2.00]	0.0000	0.65 (2.31)	0.65 (2.50)	0.0000
0.73 (0.59)	0.73 (0.53)	0.0000	0.49 (0.53)	0.50 (0.54)	-0.0187	0.58 (0.55)	0.58 (0.54)	0.0000
00 [0.00, 1.00]	1.00 [0.00, 1.00]	0.0000	0.00 [0.00, 1.00]	0.00 [0.00, 1.00]	0.0000	0.35 (0.55)	0.35 (0.54)	0.0000
1.35 (6.46)	1.58 (8.51)	-0.0304	0.78 (2.88)	0.77 (2.89)	0.0035	0.98 (4.49)	1.06 (5.57)	-0.0158
00 [0.00, 0.00]	0.00 [0.00, 0.00]	0.0000	0.00 [0.00, 0.00]	0.00 [0.00, 0.00]	0.0000	0.00 (4.49)	0.00 (5.57)	0.0000
462 (77.00/)	2 446 (76 50/)	0.0006	2.004 (25.00/)	2.006 (26.00/)	0.0002	4.546 (50.49/)	4 5 42 (50 40/)	0.0000
,402 (77.0%)	2,440 (70.5%)	0.0006	2,084 (33.8%)	2,090 (30.0%)	-0.0003	4,346 (30.4%)	4,342 (30.4%)	0.0000
0.55 (1.10)	0.57 (1.15)	-0.0178	0.22 (0.71)	0.21 (0.71)	0.0141	0.34 (0.87)	0.34 (0.89)	0.0000
00 [0.00, 1.00]	0.00 [0.00, 1.00]	0.0000	0.00 [0.00, 0.00]	0.00 [0.00, 0.00]	0.0000	0.00 (0.87)	0.00 (0.89)	0.0000
205 (12 40/)	401 (12 50/)	0.0002	752 (12 00/)	762 (12 10/)	0.0006	1 147 (12 79/)	1 164 (12 00/)	-0.0060
393 (12.4%)	401 (12.5%)	-0.0003	732 (12.970)	/03 (13.170)	-0.0000	1,147 (12.776)	1,104 (12.9%)	-0.0000
,172 (67.9%)	2,175 (68.0%)	-0.0001	2,980 (51.2%)	3,031 (52.1%)	-0.0013	5,152 (57.2%)	5,206 (57.8%)	-0.0121
761 (23.8%)	771 (24.1%)	-0.0006	1,213 (20.9%)	1,262 (21.7%)	-0.0017	1,974 (21.9%)	2,033 (22.6%)	-0.0168
,368 (42.8%)	1,331 (41.6%)	0.0019	1,458 (25.1%)	1,429 (24.6%)	0.0010	2,826 (31.4%)	2,760 (30.6%)	0.0173
536 (16.8%)	505 (15.8%)	0.0025	684 (11.8%)	672 (11.6%)	0.0006	1,220 (13.5%)	1,177 (13.1%)	0.0118
32.98 (33.52)	32.63 (41.44)		21.73 (21.64)	21.97 (23.47)	-0.0106	25.72 (26.47)	25.75 (31.06)	-0.0010
0 [13.60, 40.24]	23.21 [10.71, 40.75]	0.0263	16.93 [8.43, 28.46]	16.47 [8.00, 29.05]	0.0204	19.51 (26.47)	18.86 (31.06)	0.0225
754 (23.6%)	785 (24.5%)	-0.002	N/A	N/A	N/A	754 (23.6%)	785 (24.5%)	-0.002
,444 (76.4%)	2,413 (75.5%)	0.001	N/A	N/A	N/A	2,444 (76.4%)	2,413 (75.5%)	0.001
N/A	N/A	N/A	2,179 (37.5%)	2,153 (37.0%)	0.001	2,179 (37.5%)	2,153 (37.0%)	0.001
N/A	N/A	N/A	636 (10.9%)	629 (10.8%)	0.000	636 (10.9%)	629 (10.8%)	0.000
N/A	N/A	N/A	2,686 (46.2%)	2,711 (46.6%)	-0.001	2,686 (46.2%)	2,711 (46.6%)	-0.001
N/A	N/A	N/A	315 (5.4%)	323 (5.6%)	-0.001	315 (5.4%)	323 (5.6%)	-0.001
	0.0 [6.00, 17.00] 0.42 (0.91) 0.0 [0.00, 1.00] 0.16 (0.53) 0.0 [0.00, 0.00] 18 (0.6%) 326 (10.2%) 0.23 (1.14) 00 [0.00, 0.00] 0.73 (0.59) 10 [0.00, 1.00] 1.35 (6.46) 10 [0.00, 0.00] 462 (77.0%) 0.55 (1.10) 10 [0.00, 1.00] 395 (12.4%) 4,172 (67.9%) 761 (23.8%) 368 (42.8%) 536 (16.8%) 1.298 (33.52) 0 [13.60, 40.24] 754 (23.6%) 444 (76.4%) N/A N/A	00 [6.00, 17.00] 11.00 [7.00, 16.25] 0.42 (0.91) 0.42 (0.93) 00 [0.00, 1.00] 0.00 [0.00, 1.00] 0.16 (0.53) 0.18 (0.61) 00 [0.00, 0.00] 0.00 [0.00, 0.00] 18 (0.6%) 20 (0.6%) 326 (10.2%) 347 (10.9%) 0.23 (1.14) 0.26 (1.02) 00 [0.00, 0.00] 0.00 [0.00, 0.00] 0.73 (0.59) 0.73 (0.53) 10 [0.00, 1.00] 1.58 (8.51) 00 [0.00, 0.00] 2,446 (76.5%) 0.55 (1.10) 0.57 (1.15) 00 [0.00, 1.00] 0.00 [0.00, 1.00] 395 (12.4%) 401 (12.5%) 317 (267.9%) 2,175 (68.0%) 761 (23.8%) 771 (24.1%) 3,368 (42.8%) 1,331 (41.6%) 536 (16.8%) 505 (15.8%) 22.98 (33.52) 32.63 (41.44) 0 [13.60, 40.24] 23.21 [10.71, 40.75] 754 (23.6%) 785 (24.5%) 2,443 (75.5%) N/A N/A N/A N/A N/A N/A N/A N/A N/A	00 [6.00, 17.00] 11.00 [7.00, 16.25] -0.1087 0.42 (0.91) 0.42 (0.93) 0.0000 00 [0.00, 1.00] 0.00 [0.00, 1.00] 0.0000 0.16 (0.53) 0.18 (0.61) -0.0350 10 [0.00, 0.00] 0.00 [0.00, 0.00] 0.0000 18 (0.6%) 20 (0.6%) 0.0000 326 (10.2%) 347 (10.9%) -0.0022 0.23 (1.14) 0.26 (1.02) -0.0277 10 [0.00, 0.00] 0.00 [0.00, 0.00] 0.0000 0.73 (0.59) 0.73 (0.53) 0.0000 0.00 [0.00, 1.00] 1.00 [0.00, 1.00] 0.0000 1.35 (6.46) 1.58 (8.51) -0.0304 00 [0.00, 0.00] 0.00 [0.00, 0.00] 0.0000 3.462 (77.0%) 2,446 (76.5%) 0.0006 0.55 (1.10) 0.57 (1.15) -0.0178 00 [0.00, 1.00] 0.00 [0.00, 1.00] 0.0000 395 (12.4%) 401 (12.5%) -0.0003 3,172 (67.9%) 2,175 (68.0%) -0.0017 761 (23.8%) 771 (24.1%) -0.006 368 (42.8%) 1,331 (41.6%) 0.0019 536 (16.8%) <td< td=""> 11.00 [7.00, 1.6.25]	$\begin{array}{cccccccccccccccccccccccccccccccccccc$	$\begin{array}{c} 00 \left[6.00, 17.00 \right] & 11.00 \left[7.00, 16.25 \right] & -0.1087 & 9.00 \left[5.00, 14.00 \right] & 9.00 \left[5.00, 13.00 \right] & 0.0000 \\ 0.042 \left(0.91 \right) & 0.42 \left(0.93 \right) & 0.0000 & 0.34 \left(0.85 \right) & 0.34 \left(0.89 \right) & 0.0000 \\ 0.00 \left[0.00, 1.00 \right] & 0.00 \left[0.00, 1.00 \right] & 0.0000 & 0.00 \left[0.00, 0.00 \right] & 0.00 \left[0.00, 0.00 \right] & 0.0000 \\ 0.016 \left(0.53 \right) & 0.18 \left(0.61 \right) & -0.0350 & 0.78 \left(2.88 \right) & 0.77 \left(2.89 \right) & 0.0035 \\ 0.00 \left[0.00, 0.00 \right] & 0.00 \left[0.00, 0.00 \right] & 0.0000 & 0.00 \left[0.00, 0.00 \right] & 0.00 \left[0.00, 0.00 \right] & 0.0000 \\ 18 \left(0.6\% \right) & 20 \left(0.6\% \right) & 0.0000 & 34 \left(0.9\% \right) & 53 \left(0.9\% \right) & 0.0000 \\ 326 \left(10.2\% \right) & 347 \left(10.9\% \right) & -0.0022 & 721 \left(12.4\% \right) & 732 \left(12.6\% \right) & -0.0006 \\ 0.023 \left(1.14 \right) & 0.26 \left(1.02 \right) & -0.0277 & 1.72 \left(2.75 \right) & 1.71 \left(3.02 \right) & 0.0035 \\ 10 \left[0.00, 0.00 \right] & 0.00 \left[0.00, 0.00 \right] & 0.0000 & 1.00 \left[0.00, 2.00 \right] & 0.0000 \\ 0.73 \left(0.59 \right) & 0.73 \left(0.53 \right) & 0.0000 & 0.49 \left(0.53 \right) & 0.50 \left(0.54 \right) & -0.0187 \\ 10 \left[0.00, 0.01 \right] & 1.00 \left[0.00, 1.00 \right] & 0.0000 & 0.00 \left[0.00, 1.00 \right] & 0.00 \left[0.00, 1.00 \right] & 0.000 \\ 0.00 \left[0.00, 0.00 \right] & 0.00 \left[0.00, 0.00 \right] & 0.0000 & 0.00 \left[0.00, 0.00 \right] & 0.00 \left[0.00, 0.00 \right] & 0.0000 \\ 0.462 \left(77.0\% \right) & 2.446 \left(76.5\% \right) & 0.0006 & 2.084 \left(35.8\% \right) & 2.096 \left(36.0\% \right) & -0.0003 \\ 0.55 \left(1.10 \right) & 0.57 \left(1.15 \right) & -0.0178 & 0.22 \left(0.71 \right) & 0.21 \left(0.71 \right) & 0.0141 \\ 00 \left[0.00, 1.00 \right] & 0.00 \left[0.00, 1.00 \right] & 0.0000 & 0.00 \left[0.00, 0.00 \right] & 0.00 \left[0.00, 0.00 \right] \\ 0.00 \left[0.00, 1.00 \right] & 0.00 \left[0.00, 1.00 \right] & 0.0006 & 1.213 \left(20.9\% \right) & 3.031 \left(52.1\% \right) & -0.0013 \\ 356 \left(16.8\% \right) & 771 \left(24.1\% \right) & -0.0006 & 1.213 \left(20.9\% \right) & 3.031 \left(52.1\% \right) & -0.0013 \\ 356 \left(16.8\% \right) & 771 \left(24.1\% \right) & -0.0006 & 1.213 \left(20.9\% \right) & 1.452 \left(21.7\% \right) & -0.0107 \\ 3368 \left(42.8\% \right) & 771 \left(24.1\% \right) & -0.0006 & 1.213 \left(20.9\% \right) & 1.262 \left(21.7\% \right) & -0.0017 \\ 3368 \left(42.8\% \right) & 771 \left(24.1\% \right) & -0.0006 & 1.213 \left(20.9\% \right) & 1.262 \left(21.7\% \right) & -0.0017 \\ 3368 \left(42.8\% \right) & 7331 \left(14.6\% \right) & 0.0025 & 684 \left($	$\begin{array}{c} 0[(6.00,17.00] & 11.00[7.00,16.25] & -0.1087 & 9.00[5.00,14.00] & 9.00[5.00,13.00] & 0.0000 & 9.35(8.24) \\ 0.42(0.91) & 0.42(0.93) & 0.0000 & 0.34(0.85) & 0.34(0.89) & 0.0000 & 0.37(0.87) \\ 0.10(0.00,1.00] & 0.00[0.00,1.00] & 0.0000 & 0.00[0.00,0.00] & 0.00[0.00,0.00] & 0.0000 & 0.00[0.87] \\ 0.16(0.53) & 0.18(0.61) & -0.0350 & 0.78(2.88) & 0.77(2.89) & 0.0035 & 0.56(2.33) \\ 0.16(0.63) & 20(0.6%) & 0.0000 & 0.00[0.00,0.00] & 0.00[0.00,0.00] & 0.0000 & 0.00(2.33) \\ 18(0.6\%) & 20(0.6\%) & 0.0000 & 54(0.9\%) & 53(0.9\%) & 0.0000 & 0.72(0.8\%) \\ 326(10.2\%) & 347(10.9\%) & -0.0022 & 721(12.4\%) & 732(12.6\%) & -0.0006 & 1.047(11.6\%) \\ 0.23(1.14) & 0.26(1.02) & -0.0277 & 1.72(2.75) & 1.71(3.02) & 0.0035 & 1.19(2.31) \\ 00(0.00,0.00] & 0.00(0.00,0.00] & 0.0000 & 1.00(0.00,0.00] & 1.00(0.00,0.00] & 0.0000 & 0.65(2.31) \\ 00(0.00,0.00] & 0.07(0.59) & 0.73(0.53) & 0.0000 & 0.49(0.53) & 0.50(0.54) & -0.0187 & 0.58(0.55) \\ 00(0.00,1.00] & 1.00(0.00,1.00] & 0.0000 & 0.00(0.00,1.00] & 0.00(0.00,0.00] & 0.0000 & 0.35(0.55) \\ 1.135(6.46) & 1.58(8.51) & -0.0304 & 0.78(2.88) & 0.77(2.89) & 0.0035 & 0.98(4.49) \\ 00(0.00,0.00] & 0.00(0.00,0.00] & 0.0000 & 0.00(0.00,0.00] & 0.00(0.00,0.00] & 0.0000 & 0.34(6.65) \\ 0.55(1.10) & 0.57(1.15) & -0.0178 & 0.22(0.71) & 0.21(0.71) & 0.0141 & 0.34(0.87) \\ 0.00(0.00,1.00] & 0.00(0.00,1.00] & 0.0000 & 0.00(0.00,0.00] & 0.00(0.00,0.00] & 0.000 & 0.00(0.87) \\ 395(12.4\%) & 401(12.5\%) & -0.0005 & 2.980(51.2\%) & 3.031(52.1\%) & -0.0013 & 5,152(57.2\%) \\ 701(23.8\%) & 771(24.1\%) & -0.0006 & 1.213(2.09\%) & 1.262(21.7\%) & -0.0013 & 5,152(57.2\%) \\ 715(23.8\%) & 771(24.1\%) & -0.0006 & 1.213(2.09\%) & 1.262(21.7\%) & -0.0016 & 1.297(23.647) \\ 0(13.60,40.24) & 2.131(41.6\%) & 0.0013 & 1.438(25.1\%) & 1.647(20.9\%) & 0.0006 & 1.220(13.5\%) \\ 0(13.60,40.24) & 2.413(75.5\%) & 0.0025 & 684(11.8\%) & 672(11.6\%) & 0.0001 & 2.797(37.5\%) \\ 0(13.60,40.24) & 2.413(75.5\%) & 0.001 & N/A &$	$\begin{array}{c} 0_10(6,00,17.00) & 11.00 & (7.00,16.25) & -0.1087 & 9.00 & (5.00,14.00) & 9.00 & (5.00,13.00) & 0.0000 & 9.35 & (8.24) & 9.71 & (7.78) \\ 0.42 & (0.91) & 0.42 & (0.93) & 0.0000 & 0.34 & (0.85) & 0.34 & (0.89) & 0.0000 & 0.00 & 0.00 & (0.87) & 0.00$	</td<>	11.00 [7.00, 1.6.25]	$\begin{array}{cccccccccccccccccccccccccccccccccccc$	$\begin{array}{c} 00 \left[6.00, 17.00 \right] & 11.00 \left[7.00, 16.25 \right] & -0.1087 & 9.00 \left[5.00, 14.00 \right] & 9.00 \left[5.00, 13.00 \right] & 0.0000 \\ 0.042 \left(0.91 \right) & 0.42 \left(0.93 \right) & 0.0000 & 0.34 \left(0.85 \right) & 0.34 \left(0.89 \right) & 0.0000 \\ 0.00 \left[0.00, 1.00 \right] & 0.00 \left[0.00, 1.00 \right] & 0.0000 & 0.00 \left[0.00, 0.00 \right] & 0.00 \left[0.00, 0.00 \right] & 0.0000 \\ 0.016 \left(0.53 \right) & 0.18 \left(0.61 \right) & -0.0350 & 0.78 \left(2.88 \right) & 0.77 \left(2.89 \right) & 0.0035 \\ 0.00 \left[0.00, 0.00 \right] & 0.00 \left[0.00, 0.00 \right] & 0.0000 & 0.00 \left[0.00, 0.00 \right] & 0.00 \left[0.00, 0.00 \right] & 0.0000 \\ 18 \left(0.6\% \right) & 20 \left(0.6\% \right) & 0.0000 & 34 \left(0.9\% \right) & 53 \left(0.9\% \right) & 0.0000 \\ 326 \left(10.2\% \right) & 347 \left(10.9\% \right) & -0.0022 & 721 \left(12.4\% \right) & 732 \left(12.6\% \right) & -0.0006 \\ 0.023 \left(1.14 \right) & 0.26 \left(1.02 \right) & -0.0277 & 1.72 \left(2.75 \right) & 1.71 \left(3.02 \right) & 0.0035 \\ 10 \left[0.00, 0.00 \right] & 0.00 \left[0.00, 0.00 \right] & 0.0000 & 1.00 \left[0.00, 2.00 \right] & 0.0000 \\ 0.73 \left(0.59 \right) & 0.73 \left(0.53 \right) & 0.0000 & 0.49 \left(0.53 \right) & 0.50 \left(0.54 \right) & -0.0187 \\ 10 \left[0.00, 0.01 \right] & 1.00 \left[0.00, 1.00 \right] & 0.0000 & 0.00 \left[0.00, 1.00 \right] & 0.00 \left[0.00, 1.00 \right] & 0.000 \\ 0.00 \left[0.00, 0.00 \right] & 0.00 \left[0.00, 0.00 \right] & 0.0000 & 0.00 \left[0.00, 0.00 \right] & 0.00 \left[0.00, 0.00 \right] & 0.0000 \\ 0.462 \left(77.0\% \right) & 2.446 \left(76.5\% \right) & 0.0006 & 2.084 \left(35.8\% \right) & 2.096 \left(36.0\% \right) & -0.0003 \\ 0.55 \left(1.10 \right) & 0.57 \left(1.15 \right) & -0.0178 & 0.22 \left(0.71 \right) & 0.21 \left(0.71 \right) & 0.0141 \\ 00 \left[0.00, 1.00 \right] & 0.00 \left[0.00, 1.00 \right] & 0.0000 & 0.00 \left[0.00, 0.00 \right] & 0.00 \left[0.00, 0.00 \right] \\ 0.00 \left[0.00, 1.00 \right] & 0.00 \left[0.00, 1.00 \right] & 0.0006 & 1.213 \left(20.9\% \right) & 3.031 \left(52.1\% \right) & -0.0013 \\ 356 \left(16.8\% \right) & 771 \left(24.1\% \right) & -0.0006 & 1.213 \left(20.9\% \right) & 3.031 \left(52.1\% \right) & -0.0013 \\ 356 \left(16.8\% \right) & 771 \left(24.1\% \right) & -0.0006 & 1.213 \left(20.9\% \right) & 1.452 \left(21.7\% \right) & -0.0107 \\ 3368 \left(42.8\% \right) & 771 \left(24.1\% \right) & -0.0006 & 1.213 \left(20.9\% \right) & 1.262 \left(21.7\% \right) & -0.0017 \\ 3368 \left(42.8\% \right) & 771 \left(24.1\% \right) & -0.0006 & 1.213 \left(20.9\% \right) & 1.262 \left(21.7\% \right) & -0.0017 \\ 3368 \left(42.8\% \right) & 7331 \left(14.6\% \right) & 0.0025 & 684 \left($	$\begin{array}{c} 0[(6.00,17.00] & 11.00[7.00,16.25] & -0.1087 & 9.00[5.00,14.00] & 9.00[5.00,13.00] & 0.0000 & 9.35(8.24) \\ 0.42(0.91) & 0.42(0.93) & 0.0000 & 0.34(0.85) & 0.34(0.89) & 0.0000 & 0.37(0.87) \\ 0.10(0.00,1.00] & 0.00[0.00,1.00] & 0.0000 & 0.00[0.00,0.00] & 0.00[0.00,0.00] & 0.0000 & 0.00[0.87] \\ 0.16(0.53) & 0.18(0.61) & -0.0350 & 0.78(2.88) & 0.77(2.89) & 0.0035 & 0.56(2.33) \\ 0.16(0.63) & 20(0.6%) & 0.0000 & 0.00[0.00,0.00] & 0.00[0.00,0.00] & 0.0000 & 0.00(2.33) \\ 18(0.6\%) & 20(0.6\%) & 0.0000 & 54(0.9\%) & 53(0.9\%) & 0.0000 & 0.72(0.8\%) \\ 326(10.2\%) & 347(10.9\%) & -0.0022 & 721(12.4\%) & 732(12.6\%) & -0.0006 & 1.047(11.6\%) \\ 0.23(1.14) & 0.26(1.02) & -0.0277 & 1.72(2.75) & 1.71(3.02) & 0.0035 & 1.19(2.31) \\ 00(0.00,0.00] & 0.00(0.00,0.00] & 0.0000 & 1.00(0.00,0.00] & 1.00(0.00,0.00] & 0.0000 & 0.65(2.31) \\ 00(0.00,0.00] & 0.07(0.59) & 0.73(0.53) & 0.0000 & 0.49(0.53) & 0.50(0.54) & -0.0187 & 0.58(0.55) \\ 00(0.00,1.00] & 1.00(0.00,1.00] & 0.0000 & 0.00(0.00,1.00] & 0.00(0.00,0.00] & 0.0000 & 0.35(0.55) \\ 1.135(6.46) & 1.58(8.51) & -0.0304 & 0.78(2.88) & 0.77(2.89) & 0.0035 & 0.98(4.49) \\ 00(0.00,0.00] & 0.00(0.00,0.00] & 0.0000 & 0.00(0.00,0.00] & 0.00(0.00,0.00] & 0.0000 & 0.34(6.65) \\ 0.55(1.10) & 0.57(1.15) & -0.0178 & 0.22(0.71) & 0.21(0.71) & 0.0141 & 0.34(0.87) \\ 0.00(0.00,1.00] & 0.00(0.00,1.00] & 0.0000 & 0.00(0.00,0.00] & 0.00(0.00,0.00] & 0.000 & 0.00(0.87) \\ 395(12.4\%) & 401(12.5\%) & -0.0005 & 2.980(51.2\%) & 3.031(52.1\%) & -0.0013 & 5,152(57.2\%) \\ 701(23.8\%) & 771(24.1\%) & -0.0006 & 1.213(2.09\%) & 1.262(21.7\%) & -0.0013 & 5,152(57.2\%) \\ 715(23.8\%) & 771(24.1\%) & -0.0006 & 1.213(2.09\%) & 1.262(21.7\%) & -0.0016 & 1.297(23.647) \\ 0(13.60,40.24) & 2.131(41.6\%) & 0.0013 & 1.438(25.1\%) & 1.647(20.9\%) & 0.0006 & 1.220(13.5\%) \\ 0(13.60,40.24) & 2.413(75.5\%) & 0.0025 & 684(11.8\%) & 672(11.6\%) & 0.0001 & 2.797(37.5\%) \\ 0(13.60,40.24) & 2.413(75.5\%) & 0.001 & N/A & $	$\begin{array}{c} 0_10(6,00,17.00) & 11.00 & (7.00,16.25) & -0.1087 & 9.00 & (5.00,14.00) & 9.00 & (5.00,13.00) & 0.0000 & 9.35 & (8.24) & 9.71 & (7.78) \\ 0.42 & (0.91) & 0.42 & (0.93) & 0.0000 & 0.34 & (0.85) & 0.34 & (0.89) & 0.0000 & 0.00 & 0.00 & (0.87) & 0.00 $

^{*}Included in the 1:1 PS matching model

Optum (PS matched): https://bwh-dope.aetion.com/projects/details/1406/results/63149/result/44 Marketscan (PS matched): https://bwh-dope.aetion.com/projects/details/1407/results/63153/result/44

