	Exposure: Zoledronic acid (5 mg) 15-minute intravenous administration every year for 3 years vs. placebo Reference: Placebo Aim: To evaluate the effect of annual infusions of zoledronic acid on fracture risk during a 3-year period in postmenopausal women with osteoporosis All patients received oral daily calcium (1000 to 1500 mg) and vitamin D (400 to 1200 IU).	Exposure: new-use of Zoledronic acid (washout 450 days) NDC Generic Name: ZOLEDRONIC ACID ZOLEDRONIC ACID IN MANNITOL & WATER FOR INJECTION ZOLEDRONIC ACID IN MANNITOL AND 0.9 % SODIUM CHLORIDE ZOLEDRONIC ACID IN MANNITOL AND WATER FOR INJECTION ZOLEDRONIC ACID IN MANNITOL AND WATER FOR INJECTION NDC codes: 143964201, 16729024231, 17478032705, 25021080167, 42023015101, 43598033011, 47335003540, 47333096241, 54288010001, 5511106850755150026605, 67457039054, 68001036625, 78035084, 78038725, 409421501, 409421505, 16714081501, 17478032745, 23155017031, 25021080166, 45963044055, 51991006598, 53150087101, 60505611000, 63232096198, 68001036622, 78043561, 78059061, 409422801, 43598033111, 51991006498, 55111068852, 63323096600, 67457061910, 67457079410, 70860021051 CPT/HCPCS Procedure Codes: C9115, 13487, 13488, 13489, Q2051, Q4095 Reference of primary analysis: Raloxifene (proxy of placebo) Reference of primary analysis: Raloxifene (proxy of placebo)		Criteria	
	PRIMARY	DUTCOME		Adequate mapping in claims	
	Hip fracture (Dual-energy x-ray absorptiometry of the hip was performed at baseline and at months 6, 12, 24, and 36 for bone loss) - both patients in stratum 1 and stratum 2	Measured 1 day after drug initiation (codes reported in "Hip and femur fractures codes": Hip and femur fractures Algorithm include the following case-qualifying (CO): CQ = 1 Inpatient claim with primary diagnosis code AND CQ = 2 Inpatient claim with secondary diagnosis code AND CQ = 3 Non-inpatient claim with diagnosis code AND HCPCS in (27125, 27130, 27220, 27222, 27226-27228, 27230-27248, 27254, 27254, 27267-27269, 27500-27514) OR Non-inpatient claim with diagnosis code AND ICD-9 Procedure Code in (7855, 7905, 7915, 7925, 7935, 7965, 8151, 8152)	Wright NC, Daigle SG, Melton ME, Delzell ES, Balasubramanian A, Curtis JR. The Design and Validation of a New Algorithm to Identify Incident Fractures in Administrative Claims Data J. Bone Miner Res. 2019 Oct;34(10):1798-1807. doi: 10.1002/jbmr.3807. Epub 2019 Aug 5. PMID: 31170317.	Intermediate mapping in claims	

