HIP AND FEMUR FRACTURES CODES ICD9 Diagnosis codes (excluding rare fractures in young children) Fracture of neck of femur 820 Fracture of neck of femur 820.0 Closed fracture of intracapsular section 820.00 Closed fracture of intracapsular section of neck of femur, unspecified 820.02 Closed fracture of midcervical section of neck of femur 820.03 Closed fracture of base of neck of femur 820.09 Other closed transcervical fracture of neck of femur 820.1 Open fracture of intracapsular section of neck of femur 820.10 Open fracture of intracapsular section of neck of femur, unspecified 820.11 Open fracture of epiphysis (separation) (upper) of neck of femur 820.12 Open fracture of midcervical section of neck of femur 820.13 Open fracture of base of neck of femur 820.19 Other open transcervical fracture of neck of femur 820.2 Closed fracture of trochanteric section 820,20 Closed fracture of trochanteric section of neck of femur 820.21 Closed fracture of intertrochanteric section of neck of femur 820.22 Closed fracture of subtrochanteric section of neck of femur 820.3 Open fracture of trochanteric section 820.30 Open fracture of trochanteric section of neck of femur, unspecified 820.31 Open fracture of intertrochanteric section of neck of femur 820.32 Open fracture of subtrochanteric section of neck of femur 820.8 Closed fracture of unspecified part of neck of femur 820.9 Open fracture of unspecified part of neck of femur Fracture of other and unspecified parts of femur 821 Closed fracture 821.0 Closed fracture of femur 821.00 Closed fracture of unspecified part of femur 821.01 Closed fracture of shaft of femur convert 821.10 Open fracture of unspecified part of femur 821.11 Open fracture of shaft of femur convert 821.20 Closed fracture of lower end of femur, unspecified part 821.21 Closed fracture of condyle, femoral 821.23 Closed supracondylar fracture of femur 821.29 Other closed fracture of lower end of femur 821.3 Open fracture of lower end of femur 821.30 Open fracture of lower end of femur, unspecified part 821.31 Open fracture of condyle, femoral 821.32 Open fracture of epiphysis. Lower (separation) of femur 821.33 Open supracondylar fracture of femur 821.39 Other open fracture of lower end of femur HIP AND FEMUR FRACTURES ICD10 Diagnosis codes (incident fracture - excluding subsequent encounter and sequela, and rare fractures in young children) S72.0 Fracture of head and neck of femur (all) S72.00 Fracture of unspecified part of neck of femur S72.001 Fracture of unspecified part of neck of right femur S72.001A initial encounter for closed fracture S72.001B initial encounter for open fracture type I or II S72.001C initial encounter for open fracture type IIIA, IIIB, or IIIC S72.002 Fracture of unspecified part of neck of left femur S72.002A initial encounter for closed fracture S72.002B initial encounter for open fracture type I or II S72.002C initial encounter for open fracture type IIIA, IIIB, or IIIC S72.009 Fracture of unspecified part of neck of unspecified femur S72.009A initial encounter for closed fracture

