M84.652 Pathological fracture in other disease, left femur M84.652A..... initial encounter for fracture M84.653 Pathological fracture in other disease, unspecified femur M84.653A..... initial encounter for fracture M84.659 Pathological fracture in other disease, hip, unspecified M84.659A..... initial encounter for fracture M84.7 Nontraumatic fracture, not elsewhere classified M84.75 Atypical femoral fracture M84.750A..... initial encounter for fracture M84.751 Incomplete atypical femoral fracture, right leg M84.751A..... initial encounter for fracture M84.752 Incomplete atypical femoral fracture, left leg M84.752A..... initial encounter for fracture M84.753 Incomplete atypical femoral fracture, unspecified leg M84.753A..... initial encounter for fracture M84.754 Complete transverse atypical femoral fracture, right leg M84.754A..... initial encounter for fracture M84.755 Complete transverse atypical femoral fracture, left leg M84.755A..... initial encounter for fracture M84.756 Complete transverse atypical femoral fracture, unspecified leg M84.756A..... initial encounter for fracture M84.757 Complete oblique atypical femoral fracture, right leg M84.757A..... initial encounter for fracture M84.758 Complete oblique atypical femoral fracture, left leg M84.758A..... initial encounter for fracture M84.759 Complete oblique atypical femoral fracture, unspecified leg M84.759A..... initial encounter for fracture Fracture Aftercare ICD9 Diagnosis Codes V54.13Aftercare for healing traumatic fracture of hip V54.15 Aftercare for healing traumatic fracture of upper leg Fracture Aftercare ICD10 Diagnosis Codes S72.001D Fx unsp part of nk of r femr, subs for clos fx w routn heal S72.002D Fx unsp part of nk of I femr, subs for clos fx w routn heal S72.009D Fx unsp prt of nk of unsp femr. 7thD S72.011D Unsp intracap fx right femur, subs for clos fx w routn heal S72.012D Unsp intracap fx left femur, subs for clos fx w routn heal S72.019D Unsp intracap fx unsp femur, subs for clos fx w routn heal S72.019E Unsp intracap fx unsp femr, 7thE S72.021D Disp fx of epiphy (separation) (upper) of r femr, 7thD S72.022D Disp fx of epiphy (separation) (upper) of I femr, 7thD S72.023D Disp fx of epiphy (separation) (upper) of unsp femr, 7thD S72.023E Disp fx of epiphy (separation) (upper) of unsp femr, 7thE S72.024D Nondisp fx of epiphy (separation) (upper) of r femr, 7thD S72.025D Nondisp fx of epiphy (separation) (upper) of I femr, 7thD S72.026D Nondisp fx of epiphy (separation) (upper) of unsp femr, 7thD S72.026E Nondisp fx of epiphy (separation) (upper) of unsp femr, 7thE S72.031D Displ midcervical fx r femur, subs for clos fx w routn heal S72.032D Displ midcervical fx I femur, subs for clos fx w routn heal S72.033D Displ midcervical fx unsp femr, 7thD S72.033E Displ midcervical fx unsp femr, 7thE S72.034D Nondisp midcervical fx r femr, subs for clos fx w routn heal S72.035D Nondisp midcervical fx I femr, subs for clos fx w routn heal S72.036D Nondisp midcervical fx unsp femr, 7thD S72.036E Nondisp midcervical fx unsp femr, 7thE S72.041D Disp fx of base of nk of r femr, 7thD

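### The primary outcome is named hip fracture but defined as hip-and-femur fracture, and its printed rule does not say how a fracture from before treatment is kept from counting

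*Protocol*

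**What the plan says.** **Label.** Protocol Sections 1.3, 6.3.1 and 13.1 all call the primary outcome hip fracture. Section 6.3.1 sends the reader to Appendix A for the definition. The benchmark in Section 1.6 is the RCT's HR for hip fracture: 0.59 (0.42 to 0.83) over 3 years, about 0.745 at 18 months.

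**Rule.** The primary-outcome row of Appendix A reads "Hip and femur fractures Algorithm include the following case-qualifying", followed by three rules joined by AND:
- CQ 1: an inpatient claim with a primary diagnosis code.
- CQ 2: "Inpatient claim with secondary diagnosis code".
- CQ 3: a non-inpatient diagnosis code plus a procedure code.

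The timing is given as "Measured 1 day after drug initiation (codes reported in 'Hip and femur fractures codes". The row cites a paper on a "New Algorithm to Identify Incident Fractures in Administrative Claims Data".

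**Codes.** The ICD-9 list includes "821.01 Closed fracture of shaft of femur" and "821.3 Open fracture of lower end of femur". Atypical femoral fractures (M84.75) and stress fracture of the femoral shaft (733.97) are also listed. The ICD-10 list is headed "incident fracture - excluding subsequent encounter and sequela, and rare fractures in young children"; the ICD-9 heading excludes only rare childhood fractures. A separate block follows with ICD-9 V54.13 and V54.15 and subsequent-encounter codes, opening its ICD-10 part with "Fracture Aftercare ICD10 Diagnosis Codes S72.001D Fx unsp part of nk of r femr, subs for clos fx w routn heal". Nothing says whether these codes qualify a case, rule one out or mark an old episode.

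**Prior fracture.** None of exclusions #1 to #17 is a prior hip or femur fracture. Such a fracture enters only as a matching covariate (Appendix B). Section 13.2 lists another outcome, another comparator and an age subgroup.

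**The concern.** Two separate things are at stake.

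The first is comparability. The study asks whether claims data reproduce an RCT hip-fracture HR. An estimate for hip plus the rest of the femur, reported under a hip label, answers a somewhat different question, and no listed analysis isolates the hip.

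The second is incidence. A fracture that happened before treatment cannot be prevented by it. If such fractures are counted as events at similar rates in both arms, an HR below 1 is pulled toward 1 and the overall event risk used for power is inflated. Matching on prior fracture balances the arms, but it does not stop an old fracture from being counted as new.

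**Working it through.** **1. Reading the rule.** Taken literally, AND requires all three rules, so a single inpatient claim would not make a case. The term case-qualifying points to alternatives. Under that reading CQ 1 or CQ 2 alone suffices: one inpatient claim with a listed code in primary or secondary position, from day 1.

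**2. Which codes could recount an old fracture.** ICD-10 acute codes carry an initial-encounter marker and an incident-only heading, so they are largely guarded. ICD-9 820 and 821 carry no such marker. ICD-9 healing care has its own codes (V54.13, V54.15), which guards in part, but a later inpatient claim that still carries 820 or 821 would meet CQ 1 or CQ 2.

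**3. How many women are concerned.** In Appendix B, matched, pooled, a hip or femur fracture at baseline is recorded for 199 of 9,014 on raloxifene (2.2%) and 220 of 9,014 on zoledronic acid (2.4%). Together that is 419 of 18,028, or 2.3%. The design diagram sets the covariate window at days -450 to 0, so older fractures are outside this count.

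**4. The plan's own power.** Section 10 has E = 18,028 × 10.40/1,000 = 187.49 expected events. Power = Φ(|ln HR| × √(E/4) − 1.96). At HR 0.59: Φ(0.5276 × 6.846 − 1.96) = Φ(1.652) = 0.951, as stated in Section 10. At HR 0.745 the same formula gives 0.522.

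**5. Illustration of recounting.** The documents give no recount share, so s is an assumption. Let F = s × 419 false events be split 199:220, with total counted events held at 187.49. True events in the comparator are C = (187.49 − F)/(1 + HR). The observed HR is (HR × C + F × 220/419)/(C + F × 199/419).

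| s (assumed) | F | share of E | 0.59 reads | 0.745 reads |
|---|---|---|---|---|
| 0% | 0 | 0% | 0.590 | 0.745 |
| 2% | 8.4 | 4.5% | 0.608 | 0.759 |
| 5% | 21.0 | 11.2% | 0.635 | 0.779 |
| 10% | 41.9 | 22.3% | 0.682 | 0.814 |

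All these values lie inside the RCT interval of 0.42 to 0.83.

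**6. Cost of an analysis without the 419.** At average risk, 419 × 0.0104 = 4.4 events are lost, leaving 183.1; power at 0.59 is 0.946 and at 0.745 is 0.513. If these women carry three times the average risk (assumed), 13.1 events are lost, leaving 174.4; power is 0.936 and 0.494. If matched partners are dropped too (at most 838 women), 178.8 to 170.1 events remain; power at 0.59 is 0.941 to 0.931.

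**The case against.** The strongest reply is that the harm rests on a rule that is not printed. AND stands between the three rules, and only by reading OR does one inpatient claim suffice. This is fair, but the literal reading is hardly workable, since it would require inpatient primary, inpatient secondary and non-inpatient evidence together. Either way the connector has to be put right.

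Next, the cited algorithm was built to find incident fractures, and Appendix A refers to an online folder for missing information. A clean period may exist in either place. That stands: the documents show an incomplete printed rule, and they do not show misclassification.

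Third, including women with a prior fracture is not in itself a fault. The criteria follow the trial's, and the trial criteria listed in Appendix A contain no such exclusion. That also stands. The gap is in how the outcome is counted, not in who is enrolled.

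Fourth, Appendix A is open about using a hip-and-femur algorithm, so part of the point is a matter of naming. Naming still matters when the estimate is to be set against a hip-only HR.

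Finally, few matched women (72 + 73 = 145) were hospitalised in the 30 days to index, which limits early readmissions for a very recent fracture. It does not cover claims related to fractures earlier in the window.

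**Conclusion.** The point holds in a limited form. The name and the definition of the primary outcome differ, and the printed rule leaves open the connector, the role of the aftercare codes and any clean period. If CQ 1 to 3 are alternatives and no clean period is programmed, an inpatient ICD-9 820/821 claim for an older fracture can count as an event.

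Some stronger conclusions might be inferred, and the documents do not support them:
- That old fractures are in fact being counted. The recount share is unknown and may be zero.
- That 419 is a ceiling on the women at risk of recounting. It covers the baseline window only.
- That recounting would favour one arm materially. The arms are nearly balanced (2.2% and 2.4%), so the main effect would be a pull toward 1.
- That shaft and lower-end codes dilute the effect. Events are not given by site, so this cannot be judged.

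The HR shifts under working rest on assumed shares and are illustrations only. Confidence is medium. The point is worth settling before the comparative analysis because settling it is cheap.

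**What to change.** 1. In Appendix A, join CQ 1 to 3 with OR, state that aftercare and subsequent-encounter codes do not qualify a case, and apply and print the cited algorithm's clean period.
2. Add to Section 13.2 an analysis of the primary outcome that excludes women with a baseline hip or femur fracture.
3. Label the primary outcome hip and femur fracture, keep the cited algorithm as primary, and add a hip-only analysis (proximal femur codes) as the estimate set against the RCT hip-fracture HR.
4. Restate the events and power in Section 10 only if the overall event count changes, without looking at counts by arm.

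The cost is text edits and two analyses on data already held. The primary analysis changes only if the programming lacks a clean period. The exclusion analysis loses a little precision (power at 0.59 of about 0.946, lower if the excluded women carry higher risk) and drops any genuine second fracture in those women. The loss in the hip-only analysis cannot be sized, because events by site are not given. Section 13 shows no date for the comparative analysis, so on this text the changes can still be made before any comparative result exists.
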